**Secondary objectives:**

- Compare the second order movement of the canine (tipping) between the osteoperforation and piezocorticism procedures.
- Compare the amount of root resorption associated with the osteoperforation and piezocorticism procedures.
- Compare the inflammation process between the experimental and the control group by measuring the inflammatory markers in the gingival crevicular fluid.
- Evaluation of the loss of posterior anchorage by measures on the cone beam computed tomography (CBCT) 3-dimensional radiograph and on the casts.
- Evaluation of the pain level and the impact on quality of life following each procedure using the questionnaire of the visual analogue scale (VAS) of pain.

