**Research hypothesis:**

- Primary :
  - o The rate of canine retraction will be faster following the piezocorticisions than the osteoperforations.
- Secondary :
  - o There will be less tipping of the canine following the piezocorticisions than the osteoperforations.
  - o There will be less root resorption following the piezocorticisions than the osteoperforations.
  - o The increase in inflammation will be greater following the piezocorticisions than the osteoperforations.
  - o The posterior loss of anchorage will be less following the piezocorticisions than the osteoperforations.
  - o The pain level and the impact on quality of life will be greater following the piezocorticisions than the osteoperforations.

**Null hypothesis:** The rate of canine retraction is the same following the piezocorticisions, the osteoperforations and without any surgical procedure.

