**b) Characteristics of participants :**

*Sample size :*

- Sample size: 15 patients for the control group and 15 patients for the experimental group. A sample size of 10 subjects has a power of 80% to show a difference between the speed of retraction of the piezocorticism  $1.0 \pm 0.2/12$  weeks and the osteoperforation  $0.8 \pm 0.2\text{mm}/12$  weeks, thus a speed 20% higher for the piezocorticism, with a bilateral alpha of 0.05 and a paired sample T-test. A sample size of 15 also allows to show a difference between the experimental and control group (speed of  $0.5 \pm 0.2\text{mm}/12$  weeks), with a power of more than 80% based on an independent-sample T-test. We will recruit 15 subjects per group to compensate for the possible attrition. The sample will be 50% male, 50% female.

- Experimental group: Bilateral maxillary canine retraction after first premolar extraction with piezocorticision procedure on one side and osteoperforation on contralateral side using a split mouth design.

- Control group: Bilateral maxillary canine retraction after first premolar extraction without any surgical procedures.

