- Collection of gingival crevicular fluid samples on the distobuccal corner of the canine at 0,1, 3, 8 weeks and at the end of treatment to analyze the concentration of cytokines, IL-1, RANKL, OPG and the RANKL/OPG ratio.
- The amount of tooth movement will be measured on the digital dental casts from the tip of the canine to the third rugae palatinae.
- The amount of anchorage loss will be measured on the CBCT using the distance from the nasopalatine foramen to the projection of the mesiobuccal cusp of the first molar on the palatal suture.

**d) Measures and variables:** The rate of canine retraction (mm/12 weeks), the amount of tipping, the amount of root resorption, the amount of posterior loss of anchorage, the level of inflammation and the level of pain.

**e) Statistical analysis:** The Shapiro-Wilk test will be used to determine if the data follows the normal distribution law. A paired sample T-test and the Wilcoxon test will be used to compare the piezocorticision and the osteoperforation within the same subject for the speed of retraction, the amount of tipping, the amount of root resorption and the posterior loss of anchorage. A mixed model analysis for repeated measures (Brunner-Langer method) will be used to compare the evolution of the level of pain and the level of inflammation between the two groups through time.

**V- Expected results:** We are expecting a marked increase in the rate of canine retraction with the piezocorticision and osteoperforation procedures (two times faster than the control group). The canine retraction will be faster on the piezocorticision side than the osteoperforation side. Finally, we are expecting a more noticeable reduction in the root resorption, tipping movement and in the loss of posterior anchorage in the piezocorticision side than the osteoperforation side.

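### Pain and inflammation are compared only between two unnamed groups; read as experimental versus control, that comparison does not test the protocol's pain hypothesis about the two procedures

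*Protocol*

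**What the plan says.** Protocol section IV e (Statistical analysis) has two comparative sentences. The first names a paired t-test and a Wilcoxon test of one procedure against the other within the same patient, for four outcomes: retraction speed, tipping, root resorption and loss of posterior anchorage. The second covers pain and inflammation and uses a Brunner-Langer model "to compare the evolution of the level of pain and the level of inflammation between the two groups through time". The groups are not named.

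The questions asked of these two outcomes are set out in section III:

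- Pain, secondary objective: "Evaluation of the pain level and the impact on quality of life following each procedure".
- Pain, secondary hypothesis: "The pain level and the impact on quality of life will be greater following the piezocorticisions than the osteoperforations".
- Inflammation, secondary objective: "Compare the inflammation process between the experimental and the control group".
- Inflammation, secondary hypothesis: "The increase in inflammation will be greater following the piezocorticisions than the osteoperforations".

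Section IV b sets the design as "15 patients for the control group and 15 patients for the experimental group". Experimental patients are treated "with piezocorticision procedure on one side and osteoperforation on contralateral side using a split mouth design". Control patients have no surgical procedure.

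**The concern.** The protocol asks two different kinds of question about pain and inflammation. One compares the two procedures, which is a comparison of sides within the experimental patients. The other compares operated with unoperated patients, which is a comparison between patients. The analysis text offers one two-level comparison for both outcomes, and one such comparison cannot be both.

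At stake is whether the pain hypothesis has a pre-stated test. If the sentence is followed in its most natural sense, the trial will report whether pain differs between operated and control patients and will have no planned answer to which procedure hurts more. The side comparison could then be added, or left out, after the data are seen.

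**Working it through.** **Figures in the plan.** The plan gives no figure for pain or inflammation. Its power statement concerns retraction speed only. Taking 0.2 as the SD of the within-patient difference, the standardised difference is (1.0 − 0.8)/0.2 = 1, and a two-sided paired t-test at 0.05 with 10 patients has power 0.803, against the stated 80%. That figure reproduces and has no bearing on this point, which is about which contrast is tested.

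**Step 1: hypotheses against named tests.** Section III lists six directional hypotheses, all piezocorticision versus osteoperforation.

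| Hypothesis | Test of one procedure against the other named in IV e |
|---|---|
| Retraction speed (primary) | Paired t / Wilcoxon |
| Tipping | Paired t / Wilcoxon |
| Root resorption | Paired t / Wilcoxon |
| Loss of posterior anchorage | Paired t / Wilcoxon |
| Inflammation | None named; two-group model over time |
| Pain | None named; two-group model over time |

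Four of the six have a matching test.

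**Step 2: what the protocol means by a group.** Leaving aside the sentence in question, the word occurs 10 times: once in the secondary objectives, six times in section IV b, twice in the methods list, and once in the expected results. Each time it refers to patient groups. The power statement is one example: "A sample size of 15 also allows to show a difference between the experimental and control group". The two procedures are called sides 7 times: twice in section IV b, once in the methods list and four times in the expected results. On the protocol's own usage, the two groups are therefore the experimental and control patients. The case for the other reading is that the sentence just before compares the two procedures.

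**Step 3: each reading against each question.**

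| Question (section III) | Two groups = experimental and control | Two groups = the two procedures |
|---|---|---|
| Pain hypothesis: procedure versus procedure | Not tested | Tested |
| Inflammation hypothesis: procedure versus procedure | Not tested | Tested |
| Inflammation objective: experimental versus control | Tested | Not tested |

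Neither column covers every row. Under the first reading, each experimental patient carries both procedures, so a comparison of experimental with control patients is by definition not a comparison of one procedure with the other.

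**Step 4: are the data there?** The methods list collects visual analogue pain scores for each of the two experimental sides and for the control group. That is three conditions, so a comparison of two groups does not by itself describe the pain data. Both the side comparison and the control comparison can be made from what is already collected.

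**The case against.** The strongest reply is that section IV e is a short summary. It names the method, the outcomes and the time dimension; listing factors and contrasts is ordinary work for a statistical analysis plan, which is not available here. A Brunner-Langer model can carry a within-patient side factor as well as a group factor, and the pain data for either contrast are planned. This stands in part: a SAP could repair the matter, and no analysis is lost. It does not remove the point, because the protocol does more than leave detail open. It names a two-level comparison with no side factor, and on its own usage that comparison does not match its own pain hypothesis.

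Three stronger inferences are not supported.

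- A reader might infer that inflammation is as badly served as pain. It is not. The experimental-versus-control reading meets the inflammation objective, and the Limitations section already says that comparing the inflammatory effects of the two procedures may not be possible. That caveat does not extend to pain.
- A reader might try to express the mismatch as a loss of power, for instance by averaging the two sides and setting that average equal to control. The group test would then reject at its alpha of 5% by construction, whatever the side difference. The protocol nowhere says that sides will be averaged, and it gives no pain SD or within-patient correlation. Such figures would show nothing about this trial.
- A reader might conclude that pain should be analysed in the experimental patients alone. That would leave the control patients' pain scores, which the protocol collects, without a stated comparison.

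**Conclusion.** The point holds as a mismatch between a stated analysis and stated questions. On the protocol's own usage, the planned comparison does not test the pain hypothesis; nor does it test the inflammation hypothesis, for which the protocol already concedes doubt. On the alternative reading, the inflammation objective has no planned test.

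Its size is limited: mainly one secondary hypothesis, pain, with inflammation the lesser part. No figure in the protocol changes, and the paired comparison of retraction speed is untouched. The conclusion that the phrase means experimental and control patients rests on word usage, since the sentence does not define it; that some question goes unserved does not depend on which reading is taken. It is worth correcting because it is cheap to do before the data are seen.

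**What to change.** In section IV e, replace the unnamed groups with named contrasts.

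- **Pain.** Keep the comparison of experimental with control patients over time. Add a Brunner-Langer analysis in the experimental patients with side (piezocorticision or osteoperforation) and time both as within-patient factors, and state that this is the test of the pain hypothesis in section III.
- **Inflammation.** Name experimental versus control over time as the main contrast, in line with the secondary objective. If a side contrast is kept, label it exploratory and refer to the caveat in the Limitations section. Mark the inflammation hypothesis in section III to match.

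How a patient's two sides enter the experimental-versus-control comparison can be left to the SAP.

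The cost is wording, plus one additional secondary contrast for pain. If the inflammation side contrast is kept, there is also one exploratory contrast for each of the four named measures (IL-1, RANKL, OPG and the RANKL/OPG ratio). No new pain data are needed, and the primary comparison is unaffected.

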## VI- Schedule

Research protocol: May 2017.

Literature review: July 2017.

Scientific committee: August 2017.

Ethics committee: December 2017.

Recruitment of patients: December 2017 to January 2018.

Data collection: January 2018 to December 2018.

Redaction of the memoir: January to July 2019.

**VII – Limitations of the research:** Firstly, we will only be evaluating the efficiency of the piezocorticision and osteoperforation procedures in the specific and localized case of canine retraction. Hence, these results cannot directly be extrapolated to all types of orthodontic treatments. Secondly, the concomitant extraction of the first premolar will be contributing to the overall RAP phenomenon and thus, could confuse the analysis of our results and exaggerate the amount of reported inflammation. Finally, it is possible that we will not be able to compare the inflammatory effects of the osteoperforation and piezocorticision due to the dynamic nature of the gingival crevicular fluid and the physical proximity of both experimental sites. Still, this information will be valuable to better understand the effect of these approaches on the biological response.

## VIII – Responsibilities of the student

- Establish the research protocol.
- Create the consent form and obtain informed consent.
- Perform the orthodontic examination and the pre-treatment and post-treatment periodontal screening.
- Perform the osteoperforations and the orthodontic treatment.
- Coordinate treatment sequence with the general dentist, the

radiology and periodontology department.

- Collection of gingival crevicular fluid and inflammatory marker analysis at 0, 1, 3, 8 weeks and final.
- Gathering and analysis of the clinical, radiological and biological data.
- Redaction of the memoir.

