**Methods**

- Submission of research proposal for ethics approval.
- Recruitment of patients according to inclusion and exclusion criteria and procurement of informed consent.
- Group randomization using randomized block design.
- Pre-treatment periodontal screening consisting of a 6-point probing around each tooth, measuring of the depth of sulcus and of the distance between the marginal gingiva and the cementoenamel junction.
- Pre-treatment panoramic and cephalometric X-ray, dental impressions, intraoral and extraoral picture and elaboration of treatment plan.
- Bonding of maxillary and mandibular orthodontic brackets and initial alignment and levelling of arches.
- Surgical guide fabrication.
- Pre-retraction CBCT.
- First premolar extraction with patient's general dentist.
- Piezocorticision or osteoperforation one week following premolar extraction.
  - Preoperative rinsing with Chlorhexidine 0.12% (Peridex™) 15 mL for 60 seconds.
  - Topical anesthesia using Benzocaine 20% for 2 minutes.
  - Buccal infiltration of the maxillary canine with lidocaine, epinephrine 1 :100 000 (1,8 mL)
  - For the piezocorticision procedure ([name]): Using the surgical guide, vertical incisions are performed on the buccal mucosa, mesial and distal to the canine, starting 2 mm below the interdental papilla followed by piezocorticision cuts 3 mm deep, extending to the apex of the tooth.
  - For the osteoperforation procedure ([name]): Using the surgical guide, four osteoperforations are performed mesial and distal to the canine along the root. All perforations are 3 mm apart and 5 mm deep.
  - Prescription: Acetaminophen 500 mg q6h PRN if pain and chlorhexidine mouthwash 0.12%, 2X/day X14 days.
- Canine retraction on 0.018 X 0.025 stainless steel (SS) wire using a medium force Ni-Ti closed coil spring with force application from the canine to the molar(s), delivering a force of 150g measured with a gauge.
- Follow up every two weeks for adjustment of forces with the gauge and digital impressions.
- When the canine has reached the desired position, the post-retraction CBCT is taken.
- Evaluation of the pain level of both experimental sides and of the control group using the questionnaire of the VAS immediately after the premolar extraction, then each day for 7 days following the surgeries and the first day after each adjustment of the spring.

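### No masking of cast or CBCT readings is described, and the student who performs one of the two compared procedures is assigned the gathering and analysis of the outcome data

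*Protocol*

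**What the plan says.** Section VIII lists the student's duties. Two of them matter here: "Perform the osteoperforations and the orthodontic treatment" and "Gathering and analysis of the clinical, radiological and biological data".

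The Methods in section IV c) define the measurements. For the primary outcome, "The amount of tooth movement will be measured on the digital dental casts from the tip of the canine to the third rugae palatinae". For anchorage, "The amount of anchorage loss will be measured on the CBCT using the distance from the nasopalatine foramen" to a projected cusp of the first molar. Both sentences are in the passive and name no reader. Casts arise at the visits: "Follow up every two weeks for adjustment of forces with the gauge and digital impressions". The second scan has no fixed date: "When the canine has reached the desired position, the post-retraction CBCT is taken".

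The main comparison is split-mouth (section IV b), with one procedure on each side of the same patient. Section IV a) calls the study a randomized controlled trial and section IV c) states a randomized block design. Neither mentions masking, and the limitations in section VII do not raise it.

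**The concern.** In a split-mouth trial, anyone who knows which side had which procedure knows the allocation behind every paired difference. The student performs one of the procedures and treats the patients, so cannot be unaware of it. If that student, or any other informed person, also places the landmarks on uncoded files, reading error can become related to procedure.

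The primary outcome is a rate, that is, a change between serial casts. A side-specific reading bias that stays constant over time cancels. A bias that differs between baseline and follow-up does not, and the paired test counts it as a procedure effect. The planned difference is only 0.2 mm over 12 weeks, so a small shift could matter. It could create a false difference or hide a true one.

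This is a matter of how the data are generated. It belongs in the Methods next to the measurement rules and is not something that a statistical analysis plan would normally supply.

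**Working it through.** **1. What the text establishes**

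| Question | Where | Answer |
|---|---|---|
| Who performs osteoperforation and the orthodontic treatment? | VIII | The student |
| Who gathers and analyses clinical and radiological data? | VIII | The same student |
| Who places landmarks on casts and CBCT? | IV c) | Not stated |
| Are files coded or readers masked? | IV a), IV c), VII | Not mentioned |

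The first two rows are stated. That the student is the landmark reader is an inference from them.

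**2. Inputs for the illustration**

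- From section IV b): 1.0 against 0.8 mm/12 weeks, SD 0.2, two-sided alpha 0.05, paired t-test, n = 10 for 80% power, 15 recruited per group.
- Assumed: the SD of the paired difference, because the protocol does not say whether 0.2 is that SD or the SD of each side. With an SD of 0.2 per side and within-patient correlation ρ, it is √(2 × 0.2² × (1 − ρ)), which gives 0.200 at ρ = 0.5 and 0.283 at ρ = 0.
- Assumed: the net bias b, meaning the change in side-specific reading bias from baseline to follow-up. The protocol gives no figure. Values of 0.02, 0.05 and 0.10 mm are tried.

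**3. The protocol's own figure**

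The noncentrality is 0.2 × √10 / 0.200 = 3.16 on 9 degrees of freedom, with critical value 2.262. Power is 80.3%, which reproduces the stated 80%. With SD 0.283 it would be 51.4%.

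**4. False-positive rate when there is no true difference**

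The noncentrality is b√n / SD. For example, b = 0.05, n = 15 and SD 0.200 give 0.05 × √15 / 0.200 = 0.97; with critical value 2.145 the rejection rate is 14.7%.

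| Net bias | n = 10, SD 0.200 | n = 10, SD 0.283 | n = 15, SD 0.200 | n = 15, SD 0.283 |
|---|---|---|---|---|
| 0 | 5% | 5% | 5% | 5% |
| 0.02 mm | 5.9% | 5.5% | 6.5% | 5.8% |
| 0.05 mm | 10.9% | 7.9% | 14.7% | 9.8% |
| 0.10 mm | 29.3% | 17.1% | 43.8% | 24.8% |

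The rate reaches 10% at a net bias between 0.036 mm (n = 15, SD 0.200) and 0.065 mm (n = 10, SD 0.283).

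**5. Power for a true 0.2 mm difference when the bias opposes it**

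The noncentrality is (0.2 − b)√n / SD.

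| Opposing bias | n = 10, SD 0.200 | n = 10, SD 0.283 | n = 15, SD 0.200 | n = 15, SD 0.283 |
|---|---|---|---|---|
| 0 | 80.3% | 51.4% | 94.9% | 72.2% |
| 0.02 mm | 71.7% | 43.6% | 89.9% | 63.1% |
| 0.05 mm | 56.2% | 32.3% | 77.1% | 48.1% |
| 0.10 mm | 29.3% | 17.1% | 43.8% | 24.8% |

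With n = 15 and SD 0.200, power stays at 80% or more up to an opposing bias of 0.044 mm. With SD 0.283, power is below 80% even without bias, so reading bias would not be the main problem there.

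**The case against.** A reader might infer that the protocol has the student read the casts and scans unmasked. The documents do not support that. Gathering and analysis can mean collating and testing measurements made elsewhere. The student must also "Coordinate treatment sequence with the general dentist, the" radiology and periodontology departments, so other staff are involved. Coded files would be compatible with everything that is written. The part of the protocol missing after section VIII cannot be checked, although it follows the student's duties and does not lie in the Methods, where masking would be expected. What stands is narrower: no reader is named, nobody is masked in the text available, and the plan can be followed to the letter with an informed reader.

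A reader might also infer that the primary result will be biased, perhaps towards piezocorticision. That is not supported either. The outcome is a distance between named landmarks, not a subjective grade. No reading bias is documented, and the error rates above follow wholly from the assumed values. The largest, 0.10 mm, is half the planned difference. The direction is open: the hypothesis in section III favours piezocorticision, while the student performs the other procedure. All of this limits what can be said about harm. It does not remove the case for a cheap safeguard.

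Finally, coding has limits of its own. Undated casts read in random order could make the same third ruga harder to find on each cast and add random error. The two-weekly force adjustments also remain unmasked. The first can be handled in how the files are presented; the second cannot be handled by coding.

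**Conclusion.** The concern holds in limited form. The text available describes no masking of cast or CBCT readings and assigns gathering and analysis of those data to the student who performs one of the compared procedures. It therefore leaves the primary outcome and anchorage loss open to reading by someone who knows each side's procedure. Whether that would happen, and with what bias, cannot be determined.

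The size is illustrative only. With n = 10 to 15 and an SD of the paired difference of 0.20 to 0.28, a net bias of 0.05 mm, a quarter of the planned effect, takes the false-positive rate from 5% to about 8–15%. A net bias of 0.02 mm leaves it at 5.5–6.5%, which is nearly harmless. The protocol should be changed because the safeguard is cheap, not because bias has been shown. Confidence is medium.

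**What to change.** Name the reader in section IV c) and add, next to the measurement rules, wording to this effect:

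> Before measurement, cast and CBCT files are coded, stripped of patient identity and procedure information, and randomly mirrored left-right. The key is held, until all measurements are locked, by a team member who neither performs the procedures nor takes the measurements. One patient's casts may be read together as a coded set, all mirrored the same way, so that the same third ruga is identified on each.

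The same student may still measure, so no extra reader is needed. A reader who did not treat the patients would be better masked, if one is available.

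**Cost.** A short coding step per file:

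- Casts: 30 patients × 2 = 60 if only baseline and 12-week casts are masked, or 30 × (1 + 6) = 210 for all two-weekly casts to 12 weeks. Both counts assume one baseline digital cast per patient. The Methods set no 12-week limit on the visits, so there would be more if later casts are measured.
- CBCT: 30 × 2 = 60 scans, before and after retraction.

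**Downside.** Masking is partial. The treating student may recognise a dentition or surgical marks; mirroring makes the side harder to identify but does not guarantee that it is hidden. Coding also does not mask the two-weekly force adjustments.
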